5.5 Treatment Assignment Procedures

Participants will be assigned to either combination letrozole and clomid or letrozole monotherapy in a 1:1 allocation ratio. Randomization will be blocked (with random sequences of block sizes 2, 4 and 6) and stratified by age ($< 35 \text{ versus} \ge 35$), body mass index ($< 30 \text{ and } \ge 30$), and site to ensure that balance between the treatment groups within age, BMI, and site is maintained over the enrollment period.

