trial of letrozole alone versus combination of letrozole and clomiphene citrate (CC) for up to 3 treatment cycles. Letrozole dosing will be increased in a stair-step fashion based on ovulation results. Participants will return for a mid-luteal ultrasound and progesterone lab to determine ovulatory status. Women will be randomized in a 1:1 ratio and the randomization scheme will be coordinated through the UIHC. Randomization will be stratified by site, age and BMI. The primary analysis will use an intent-to-treat approach to evaluate ovulatory rate in the

two treatment arms.

Objectives: To determine efficacy and safety of the combination letrozole and CC compared to letrozole alone in achieving ovulation in

infertile women with anovulation.

Primary Outcome: Ovulation will be the primary outcome determined by a mid-luteal progesterone level ≥ 3 and cumulative ovulation rate will be the primary efficacy parameter.

Secondary Outcome: Secondary efficacy parameters will include pregnancy rate (conception and clinical pregnancy), live birth rate, multiple gestation live birth rate, pregnancy loss rate (biochemical, miscarriage, ectopic) and time to pregnancy.

Side effect profile and complication rate will be monitored and reported.

Obstetric outcomes will include pregnancy complication rate, birth weight and sex, neonatal complication rate.

Ultrasound findings will be reported and compared between the two groups including: number of corpora lutea and endometrial thickness.

ClinicalTrials.gov Identifier

201906826

Population: 184 healthy women infertile women with polycystic ovary

syndrome or normogonadotropic normoestrogenic anovulation or oligo-ovulation, age \geq 18 to \leq 40. Additionally, the couple will

have no other major infertility factor.

Phase: IV

Number of Sites: 4 sites

University of Iowa Hospitals and Clinics Iowa City, IA with 2 ancillary sites

- Quad Cities Clinic, Davenport, IA
- Jordan Creek Clinic, Des Moines, IA

University of Wisconsin, Generations Clinic, Middleton, WI

Description Intervention:

of 184 women will be equally randomized to two different treatment arms at time of menses (spontaneous or induced with progestin withdrawal) or random start: A) letrozole 2.5 mg every day for 5 days (days 3-7 of cycle), or B) letrozole 2.5 mg and clomiphene citrate 50 mg every day for 5 days (days 3-7 of cycle), for a total of up to 3 treatment cycles.

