As previously mentioned, this is an open trial. Patient will be aware of the treatment intervention they are receiving. Currently, letrozole is considered the current standard of care/first line agent for WHO class II anovulation (women with PCOS). Both groups will be receiving at minimum the current standard of care treatment.

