5.5.1 Randomization Procedures

Participants will be randomized using randomization tables generated by a statistician and uploaded to the project in RedCap. The randomization scheme will not be accessible to study staff in order to maintain allocation concealment. Study staff will randomize subjects by entering BMI category (<30 or 30+), age category (<35 or 35+) and site on the RedCap Randomization page. Once these fields are entered and confirmed to be accurate, staff will click the "Randomize" button under treatment group to receive the participants assigned treatment."

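### Printing block sizes 2, 4 and 6 in an open-label protocol lets site staff who track past assignments partly predict the next arm, although the list itself is hidden

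*Combined protocol and SAP*

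**What the plan says.** Section 5.5 assigns women "in a 1:1 allocation ratio" and states that "Randomization will be blocked (with random sequences of block sizes 2, 4 and 6) and stratified by age", BMI and site. The probability of each block size is not given.

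Section 5.5.1 describes the procedure: "Study staff will randomize subjects by entering BMI category (<30 or 30+), age category (<35 or 35+) and site on the RedCap Randomization page". They then click a button and receive the arm. The protection offered there is that "The randomization scheme will not be accessible to study staff in order to maintain allocation concealment". Section 4.1 adds that randomization is central and computer-based, and section 5.5 varies the block order at random. Nothing in the documents withholds the block sizes from sites.

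Section 4.1 is plain about blinding: "As previously mentioned, this is an open trial. Patient will be aware of the treatment intervention they are receiving". Section 6.2 has a study team member dispense the drug. Under section 11, sites enter their own data in REDCap and can see their own records.

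**The concern.** Hiding the list conceals the next assignment only if it cannot be inferred from earlier ones. Every permuted block ends in balance, so within a stratum the arm that is behind is always the more likely next one. In an open trial the running tally can be known at the site. Printing the sizes tells staff when a guess is strong, and a block of 2 makes the assignment after the first one in a block often predictable.

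The risk is selection bias: deciding whom to approach, or when to schedule the baseline visit, in the light of the expected arm. The documents leave some room for this. Staff review clinic schedules and approach patients (section 5.4), random starts are allowed and progestin withdrawal is partly discretionary (section 4.2), and screening may fall on the baseline day (Appendix A). The protocol also reports a nearly doubled ovulation rate with the combination in the pilot, so staff may hold a preference.

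The primary analysis is an unadjusted intention-to-treat chi-square test (sections 12.1.3 and 12.2). Adjustment, if needed, covers site, prior exposure, age and BMI. Prognostic selection on other traits would remain.

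**Working it through.** **Inputs.** Block sizes 2, 4, 6 and 1:1 allocation (5.5); four sites (Protocol Summary); two age and two BMI categories (5.5.1); 184 women (12.1.4). Strata: 4 × 2 × 2 = 16. Average stratum: 184/16 = 11.5, so 11 and 12 are both shown. Assumption: the three sizes are equally likely; other mixes follow below.

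**The plan's own figure.** The documents give no predictability figure. The sample size that sets the stratum size does reproduce. Taking 60% v 80% (the control rate is not stated), two-sided 0.05 and 80% power, n = [1.96√(2 × 0.7 × 0.3) + 0.842√(0.24 + 0.16)]² / 0.2² = 81.2, so 82. Then 82/0.9 = 91.1, so 92 per arm and 184 in total.

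**Second woman in a stratum.** In a block of size s, the chance that she gets the arm opposite to the first woman is (s/2)/(s − 1).
- Sizes 2/4/6: (1 + 2/3 + 3/5)/3 = 0.756.
- Sizes 4/6/8: (2/3 + 3/5 + 4/7)/3 = 0.613.

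**Long-run accuracy of guessing the arm that is behind.** Expected correct guesses per block are 1.5, 2.833 and 4.1 for sizes 2, 4 and 6.
- Equal mix: (1.5 + 2.833 + 4.1)/(2 + 4 + 6) = 8.433/12 = 0.703. The same calculation for 4/6/8 gives 0.681.
- Probability proportional to size: (2 × 1.5 + 4 × 2.833 + 6 × 4.1)/(2² + 4² + 6²) = 38.93/56 = 0.695.
- Probability inversely proportional to size: (1.5/2 + 2.833/4 + 4.1/6)/(1 + 1 + 1) = 2.142/3 = 0.714.

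This average therefore depends little on the mix. The guess also needs no knowledge of the sizes; knowing them mainly tells staff which guesses are strong.

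**Exact enumeration within a stratum.** For every assignment history, the probability of the next arm was updated over block size and position, as an observer who knows the sizes could do. With equal mix:

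| Measure | 2/4/6 | 4/6/8 |
|---|---|---|
| Best guess right, 11 to 12 per stratum | 68–69% | 65–67% |
| Callable at ≥80%, 11 to 12 per stratum | 41–45% | 16–17% |
| Callable at ≥70%, 12 per stratum | 58% | 51% |
| Callable at ≥75%, 12 per stratum | 58% | 40% |
| Callable at ≥82%, 12 per stratum | 26% | 15% |
| Callable at ≥85%, 12 per stratum | 14% | 10% |
| Callable at ≥90%, 12 per stratum | 7% | 3% |

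Eight strata of 11 and eight of 12 (88 + 96 = 184) give 43% at ≥80% for 2/4/6. Those calls are right about 85% of the time, and about 3% of assignments are fully certain.

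**Other size mixes, share callable at ≥80% with 12 per stratum (2/4/6 v 4/6/8).** Proportional to size: 29% v 15%. Equal: 45% v 17%. Inversely proportional: 56% v 29%. With 11 per stratum the proportional mix gives 28% for 2/4/6, so the range is about 28–56%.

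**Theoretical bias.** Assume, for illustration only, that staff can choose between women whose ovulation chances differ by 20 points, and that every best guess is acted on. The induced difference between arms is (2 × accuracy − 1) × 20.
- 2/4/6: (2 × 0.693 − 1) × 20 = 7.7 points.
- 4/6/8: (2 × 0.665 − 1) × 20 = 6.6 points.
- With a quarter of guesses acted on: 1.9 v 1.7 points.

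The change of sizes removes (7.7 − 6.6)/7.7 = 14% of this.

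**The case against.** The strongest reply is that the apparent benefit depends on the cut-off. Many of the 2/4/6 probabilities lie just above 0.80, where the gap is 28 points; at 85% it is 4 points, and average accuracy differs by less than 3. This stands. A reader might count only calls above 80%, credit each at exactly 80%, and infer a full-steering bias of 5.4 v 2.0 points. That treats every weaker guess as harmless, and most of the usable guesses under 4/6/8 are of that kind, so the comparison should not be used.

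Three other tempting readings also fail.
- *The 16 strata cause the problem.* They do not: the same blocks stratified by site alone give about 50% callable at ≥80%. Sixteen tallies are also harder to track.
- *The same people screen, randomise and dispense.* The documents name several possible roles and do not say so.
- *Steering will happen.* Randomization follows consent, an eligibility check and a negative pregnancy test (7.2). Baseline is tied to the first cycle days, or to a random start within a week of ultrasound and progesterone (7.1). Section 4.2 also specifies progestin withdrawal after more than three months without menses. The room to manoeuvre is limited, and the documents show only that it exists.

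The defence that size-2 blocks are needed for balance within small strata carries little weight. The largest imbalance in an unfinished block is half the largest block size: 6/2 = 3 now, 8/2 = 4 with 4/6/8.

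**Conclusion.** The point holds as a modest, avoidable weakness in concealment, not as a design error. Hiding the list does not fully conceal the next assignment when the sizes are printed, assignments are open and blocks are as small as 2. The most stable summary is best-guess accuracy of about 68–69% against 50%. The 41–45% callable at ≥80% certainty rests on equally likely sizes, 11 to 12 women per stratum, and staff who keep a tally by stratum. It should be quoted with its range (28–56% across mixes) and its sensitivity to the cut-off (about 14% at ≥85% with equal mix). Larger blocks mainly reduce confident calls, the ones staff could most readily act on. Priority: consider.

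**What to change.** In section 5.5, replace the stated sizes with wording such as *randomly varying block sizes held by the statistician*, and record the sizes and their probabilities in a restricted randomisation file. Generate the REDCap tables without size-2 blocks, for example with 4, 6 and 8 in random order. Using only 4 and 6 would bring the ≥80% share down to about 30%, against about 16% with 4, 6 and 8. If enrolment has begun, change only the unused part of the tables. This still helps sites that have seen the printed sizes, because those sizes would no longer apply.

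The strata, 1:1 ratio, sample size and REDCap workflow stay as they are. The cost is one protocol sentence, a new table upload, and a possible imbalance of 4 instead of 3 in an unfinished block. Withholding the sizes does not stop the simple guess of the arm that is behind, so some predictability will remain.

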5.5.1 Randomization Procedures

Participants will be randomized using randomization tables generated by a statistician and uploaded to the project in RedCap. The randomization scheme will not be accessible to study staff in order to maintain allocation concealment. Study staff will randomize subjects by entering BMI category (<30 or 30+), age category (<35 or 35+) and site on the RedCap Randomization page. Once these fields are entered and confirmed to be accurate, staff will click the "Randomize" button under treatment group to receive the participants assigned treatment."

5.6 Subject Withdrawal

Subjects may withdraw voluntarily from the study or the investigator may terminate a subject's participation.

5.6.1 Reasons for Withdrawal

Subjects are free to withdraw from participation in the study at any time upon request.

An investigator may terminate a study subject's participation in the study if:

- Any clinical adverse event (AE), laboratory abnormality, or other medical condition or situation occurs such that continued participation in the study would not be in the best interest of the subject.
- The subject meets an exclusion criterion (either newly developed or not previously recognized) that precludes further study participation.
- The study is terminated

6 STUDY INTERVENTION

6.1 Study Product Description

Study medications, letrozole and clomiphene citrate will be purchased through the University of Iowa Research pharmacy. Letrozole comes in 2.5 mg tablets and CC comes in 50 mg tablets.

6.1.1 Formulation, Packaging, and Labeling

Letrozole will be packaged based on dosage indicated per the study protocol. Letrozole 2.5 mg (5 total tablets) will be supplied for the first cycle for all participants. Letrozole dose will be increased if patient did not ovulate on the dose prescribed or had significantly delayed ovulation based on the protocol. If prescribed Letrozole 5.0 mg, 10 tablets will be prescribed and if prescribed Letrozole 7.5 mg, 15 tablets will be prescribed. The total dosage per cycle needed will be provided in one vial with a medication label.

If the patient is in the combined group, they will receive letrozole mediation as above and also receive CC 50 mg (5 tablets). This will be packaged in its own vial with a medication label.

All medications will be dispensed in containers which meets the requirements of the Poison Prevention Packaging Act of 1970, 15 U.S.C. ss. 1471-1476 (2001), unless otherwise requested by the subject, and of Section 502G of the Federal Food, Drug and Cosmetic Act, 21 U.S.C. ss. 301 et seq. (2001).

Preprinted adhesive medication labels will be affixed to the container(s) in which the drug is dispensed. Labels will include: name, address, and phone of prescribing physician; name of patient; date dispensed; directions for administering the prescription medication; expiration date, and name and strength of the prescription drug in the container. Labels will be edited by each site to comply with local regulations. Example labels where patient name, dispense date and prescribing physician and location can be filled when dispensing are as follows:

Clomiphene 50mg:

Name:	Date:
Take 1 tablet daily on cycle days 3 Clomiphene Citrate tablets 50 mg	•
CLC II Study Dr:	
UIHC-[name]	[contact]

Date:

Letrozole 2.5mg:

Name:

Take 1 tablet daily on cycle days 3 through 7. Letrozole tablets 2.5 mg Total tabs #5

CLC II Study Dr:

UIHC-[name] [contact]

Letrozole 5.0mg:

Name: Date:

Take 2 tablets daily on cycle days 3 through 7. Letrozole tablets 2.5 mg Total tabs #10

CLC II Study Dr:

UIHC-[name] [contact]

Letrozole 7.5mg:

Name: Date:

Take 3 tablets daily on cycle days 3 through 7. Letrozole tablets 2.5 mg Total tabs #15

CLC II Study Dr:

UIHC-[name] [contact]

6.1.2 Product Storage and Stability

Study medications will be stored at each site in a locked room in a locked cabinet and be inaccessible to unauthorized personnel. Study medication will be stored at room temperature, with temperature tracked by a min/max thermometer with temperatures recorded weekly in a temperature log.

Letrozole should be stored at 20° to 25°C (68° to 77° F) and Clomid at 15° to 30°C (59° to 86° F).

Expiration date from the original vial will be included on the medication label. Prior to dispensing, dispenser will ensure expiration time has not elapsed prior to dispensing.

At University of Wisconsin storage of the drugs will be according to the UW Health Administrative (non-clinical) Investigational and Study Drug Control policy.

6.2 Administration of Study Product

University of Iowa Study Team will deliver medication to satellite recruiting clinics.

The medication will be dispensed to the patient by one of Study Team members. Verification of correct tablet number, correct packaging and expiration date will be performed prior to dispensing.

6.3 Accountability Procedures for the Study Product

All received and dispensed medications will be documented on medication logs maintained by each study site. Record logs must comply with applicable regulations and guidelines and should include:

- Drug name and strength, Manufacturer, and Lot Number
- Date and Quantity Received
- Date and Quantity Dispensed, Subject ID, Name of prescriber, and Dispenser's initials
- Date and Quantity Returned by Subject
- Date and Quantity Stock Destroyed
- Dates and Findings of Inventory Checks

6.4 Assessment of Participant Compliance with Study Product Administration

Participant compliance will be assessed with questionnaires and pill counts. Participants will be asked to report the number of pills taken per day on their journal log. Participants will also be asked to bring their pill bottles with any remaining medication to their midluteal and end-of-treatment visits. Study staff will perform pill counts at each study visit. Study staff will perform pill counts outside of the room where the participant is located when possible.

7 STUDY SCHEDULE

A diagram of the Schedule of Events is provided in Appendix A.

7.1 Screening

Screening Visit

- Obtain and document consent from potential subject on screening consent form.
- Review medical history to determine eligibility based on inclusion/exclusion criteria.
- Review medications history to determine eligibility based on inclusion/exclusion criteria.
- Review when to schedule study enrollment visits for individuals who are eligible and available for the duration of the study.
 - Cycle day 1-3 or
 - At random once pregnancy and recent/imminent ovulation and follicular development are excluded (no follicular development on ultrasound and anovulatory progesterone) (within a week of these studies)
- At University of Wisconsin, A consenting visit will be scheduled on a day when the
 potential subject has availability, after she has reviewed the consent form. This
 visit will be done by video conferencing so the coordinator can witness the subject
 signing the consent form.
 - Ouring the remote visit, if eligibility has been confirmed, the coordinator may complete informed consent. The identity of the subject will be verified during the e-visit that will be set up for remote consenting. During this visit, conducted via video conference, the coordinator will ask the patient to say her name and DOB to identify herself. Confirmation of the subject's identity can be recorded in a memo in the patient's study record. The subject will electronically sign the consent form through DocuSign. Email permission will be obtained before sending the electronic consent form to the potential participant as there is an email permission comment in the phone script,
 - The date and time of the consent, along with the people who are present and the method of consent, will be documented in a memo for each subject. Upon receipt of the signed consent form, the coordinator will complete the consent by signing and dating both forms. At this point, the subject is enrolled. The coordinator will contact the clinical staff about the enrolled subject.

7.2 Enrollment/Baseline

The enrollment/baseline visit will be scheduled when participants are on Cycle day 1-3 of their cycle or when ready to begin taking medication after pregnancy and recent/imminent ovulation have been excluded. All participants must have a negative urine pregnancy test prior to randomization.

Enrollment/Baseline Visit (Cycle Day 1-3 or at random as noted above)

- Obtain and document consent from subject on study consent form.
- Verify inclusion/exclusion criteria.
- Obtain a urine pregnancy test and confirm negative result.
 - Participation will be concluded at this point for participants with a positive urine pregnancy test; however, if a miscarriage results, participants can continue participation
- Review medical history and record in participants record in RedCap
- Assign participant ID
 - Participants IDs are assigned sequentially by site, with a 5 digit ID comprised of two components:
 - The first 2 digits of the ID are assigned based on the participant's primary study site:

Iowa City: 01

Quad Cities: 02

University of Wisconsin: 03

• Des Moines: 04

- The final 3 digits of the ID are assigned based on where the participant falls sequentially in enrollment at that site.
 - Ex. The first participant at lowa city would be 01001, the second at this site 01002, the third 01003 etc.
 - The next sequential number for the site can be identified by viewing the "Participants enrolled" report in RedCap and filtering on the participant's primary site. The assigned number should follow the final number on the report for that sites sequence.
- Randomize participant in RedCAP to determine treatment allocation

- Dispense study medication for initial cycle
- Review instructions on how to complete the calendar log and how to take study medication
 - Participants should complete the calendar log to document sexual activity, side effects, and LH surge beginning the first day they take the study medication. Calendar logs are available on RedCAP and weekly links for the calendar log will be sent to the participant's email after randomization. Subjects who do not wish to complete the calendar log electronically will have the option of completing on paper and returning to study staff at their next visit.
 - Participants should take the study medication on cycle day 3 through 7 for a total of 5 days. If participants are unable to begin the medication on cycle day 3, they may begin on cycle day 4 or 5, but should begin medication no later than cycle day 5. Participants who meet criteria for random start will take the medication for 5 days at random start, with the first day of medication considered cycle day 3.
- Have participant complete baseline questionnaires (GAD7, PHQ9, FertiQoL, and Perceived Stress Scale, or if participant prefers to complete online, provide instructions on completing forms after visit
- Obtain a consent to obtain medical information from the participant if medical records will need to be obtained from an external provider for either fertility treatment chart abstraction and/or for potential future pregnancy chart abstraction

7.3 Intermediate Visits

Participants will return for a midluteal study visit on cycle day 21-24 or 7-9 days following positive ovulation prediction test to determine if ovulation occurred. This visit will include an ultrasound and a progesterone lab.

If there is no ovulation, the daily dose of letrozole will be increased by 2.5 mg, to begin immediately. During the first cycle after letrozole dose increase, participants would receive 5mg daily for 5 days. If participants receive a second letrozole dose increase, they would receive 7.5 mg Letrozole daily for 5 days. The maximum dose for Letrozole in this study is 7.5 mg. CC 50 mg will be given on the same days as the letrozole in all cycles in the combination arm. Midluteal visits will be performed in all cycles. Each participant will complete a maximum of 3 cycles of medical therapy. On average we expect this to be about 4 months time, however, delayed ovulation, a biochemical pregnancy, or 1st trimester pregnancy loss in the first or second treatment cycle could delay the start of subsequent cycles, and therefore would extend active participation.

Cycle 1 Midluteal Visit

Timing will be based on LH testing, ideally around 7-8 days post-positive test or CD21-24 if no positive test

- Transvaginal ultrasound to assess for corpora lutea and endometrial thickness and pattern
- Serum progesterone assessment for ovulation
- Review subject calendar log and record adverse events as reported by subject or observed by investigator.
- Determine dosage for next cycle based on ultrasound and progesterone results and record in RedCap
 - If there is no ovulation, the daily dose of letrozole will be increased by 2.5 mg (5mg). The combination arm will continue to receive CC 50mg along with the increased letrozole dose.
 - If there is ovulation, treatment will be repeated in the next cycle with the same dose of letrozole. The combination arm will continue to receive CC 50mg along with letrozole 2.5mg.
- Schedule a follow up Progesterone lab if necessary
 - Participants with anovulatory progesterone levels (<3 ng/ml) and evidence of follicular development will return for a repeat progesterone level assessment in 10-14 days.
 - Participants with elevated anovulatory progesterone levels (1.5 < P4 < 3.0) and corpus luteum on ultrasound will return for a repeat progesterone level assessment in 2-3 days
- Dispense pregnancy test and medication for next cycle and review instructions for medication (dispense medication if unable to return to pick up meds, if can easily return, have participant return for med pick up)
 - Participants without ovulation nor evidence of follicular development are to complete pregnancy test and begin medication at new dose immediately following negative pregnancy test
 - Participants with ovulation are to wait until onset of menses, or two weeks after midluteal visit to complete pregnancy test. They can begin medication at same dose following negative pregnancy test. Participants with a positive pregnancy test will be moved to pregnancy track and will return dispensed medication at their next study visit.

- Collect any unused medication from current cycle and document participant compliance in RedCap
- Record results of ultrasound and serum progesterone in RedCap

Cycle 1 Follow-up Midluteal Visit*

Participants with anovulatory progesterone levels (<3 ng/ml) and evidence of follicular development at their midluteal visit will return for a repeat progesterone level assessment in 10-14 days. This can be performed at a local lab if the participant prefers.

- Serum progesterone assessment for ovulation
- Review subject calendar log and record adverse events as reported by subject or observed by investigator.
- Review instructions for previously dispensed medication/dispense medication if not yet dispensed
 - Participants without ovulation are to complete pregnancy test and begin medication at new dose following either a spontaneous menses or withdraw bleed and a negative pregnancy test. They can begin taking medication to induce a withdraw bleed on cycle day 35, following a negative pregnancy test.
 - Participants with ovulation are to wait until onset of menses, or two weeks after midluteal visit to complete pregnancy test. They can begin medication at new dose following negative pregnancy test (if ovulation did not occur on or before cycle day 21). Participants with a positive pregnancy test will be moved to pregnancy track and will return dispensed medication at their next study visit.
 - Participants who were initially anovulatory at a study visit prior to cycle day 21, who are ovulatory at a follow up visit by cycle day 21 will be maintained on the same dose of medication. This may occur if participant's study visit was moved up due to an early false positive ovulation prediction test.
- Record results of serum progesterone in RedCap

Cycle 1 Menses Check-In/Cycle 2 Start (menses from Cycle 1)*

Two weeks post Midleuteal visit if no menses before then

Participants with ovulation are to wait until onset of menses, or two weeks after midluteal visit to complete pregnancy test. They can begin medication at new dose following negative pregnancy test. This visit can be completed remotely with participant logging information in RedCap. If they don't have medication, they will come in to pick it up. Participants with a positive pregnancy test will be moved to pregnancy track and will return dispensed medication at their next study visit.

Cycle 2 Midluteal Visit

Timing will be based on LH testing, ideally around 7-8 days post-positive test or CD21-24 if no positive test.

- Transvaginal ultrasound to assess for corpora lutea and endometrial thickness and pattern
- Serum progesterone assessment for ovulation
- Review subject calendar log and record adverse events as reported by subject or observed by investigator.
- Determine dosage for next cycle based on ultrasound and progesterone results and record in RedCap
 - If there is no ovulation, the daily dose of letrozole will be increased by 2.5 mg.
 - Participants on Letrozole 2.5 this cycle will be increased to Letrozole 5.0 in cycle 3.
 - Participants on Letrozole 5.0 this cycle will be increased to Letrozole
 7.5 in cycle 3.
 - The combination arm will continue to receive CC 50mg along with the increased letrozole dose.
 - If there is ovulation, treatment will be repeated in the next cycle with the same dose of letrozole. The combination arm will continue to receive CC 50mg along with either Letrozole 2.5 or 5.0.
- Schedule a follow up progesterone lab if necessary
 - Participants with anovulatory progesterone levels (<3 ng/ml) and evidence of follicular development will return for a repeat progesterone level assessment in 10-14 days (lab can be done locally or at clinic site).

- Participants with elevated anovulatory progesterone levels (1.5 < P4 < 3.0) and corpus luteum on ultrasound will return for a repeat progesterone level assessment in 2-3 days
- Dispense pregnancy test and medication for next cycle and review instructions for medication
 - Participants without ovulation nor evidence of follicular development are to complete pregnancy test and begin medication at new dose immediately following negative pregnancy test
 - Participants with ovulation are to wait until onset of menses, or two weeks after midluteal visit to complete pregnancy test. They can begin medication at same dose following negative pregnancy test. Participants with a positive pregnancy test will be moved to pregnancy track and will return dispensed medication at their next study visit.
- Collect any unused medication from current (or previous) cycle and document participant compliance in RedCap
- Record results of ultrasound and serum progesterone in RedCap

Cycle 2 Follow-up Midluteal Visit*

Participants with anovulatory progesterone levels (<3 ng/ml) and evidence of follicular development at their midluteal visit will return for a repeat progesterone level assessment in 10-14 days. This can be performed at a local lab if the participant prefers.

- Serum progesterone assessment for ovulation
- Review subject calendar log and record adverse events as reported by subject or observed by investigator.
- Review instructions for previously dispensed medication
 - Participants without ovulation are to complete pregnancy test and begin medication at new dose immediately following negative pregnancy test
 - Participants with ovulation are to wait until onset of menses, or two weeks after midluteal visit to complete pregnancy test. They can begin medication at new dose (if ovulation did not occur on or before cycle day 21) following negative pregnancy test. Participants with a positive pregnancy test will be moved to pregnancy track and will return dispensed medication at their next study visit.

Participants who were initially anovulatory at a study visit prior to cycle day 21, who are ovulatory at a follow up visit by cycle day 21 will be maintained on the same dose of medication. This may occur if participant's study visit was moved up due to an early false positive ovulation prediction test.

0

Record results of serum progesterone in RedCap

Cycle 2 Menses Check-In/Cycle 3 Start (menses following Cycle 2)*

Two weeks post Midleuteal visit if no menses before then

Participants with ovulation are to wait until onset of menses, or two weeks after midluteal visit to complete pregnancy test. They can begin medication at new dose following negative pregnancy test. This visit can be completed remotely with participant logging information in RedCap. Participants with a positive pregnancy test will be moved to pregnancy track and will return dispensed medication at their next study visit.

Cycle 3 Midluteal Visit

Timing will be based on LH testing, ideally around 7-8 days post-positive test or CD21-24 if no positive test.

- Transvaginal ultrasound to assess for corpora lutea and endometrial thickness and pattern
- Serum progesterone assessment for ovulation
- Review subject calendar log and record adverse events as reported by subject or observed by investigator.
- Schedule a follow up ultrasound if necessary
 - Participants with anovulatory progesterone levels (<3 ng/ml) and evidence of follicular development will return for a repeat progesterone level assessment in 10-14 days.
- Dispense pregnancy test review instructions for study completion
 - Participants with ovulation are to wait until onset of menses, or two weeks after midluteal visit to complete pregnancy test. Participants with a positive pregnancy test will be moved to pregnancy track.

 Collect any unused medication from current or previous cycles and document participant compliance in RedCap

Record results of ultrasound and serum progesterone in RedCap

Cycle 3 Follow-up Midluteal Visit*

Participants with anovulatory progesterone levels (<3 ng/ml) and evidence of follicular development at their midluteal visit will return for a repeat progesterone level assessment in 10-14 days. This can be performed at a local lab if the participant prefers.

- Serum progesterone assessment for ovulation
- Schedule a follow up Progesterone lab if necessary
 - Participants with anovulatory progesterone levels (<3 ng/ml) and evidence of follicular development will return for a repeat progesterone level assessment in 10-14 days.
 - Participants with elevated anovulatory progesterone levels (1.5 < P4 < 3.0) and corpus luteum on ultrasound will return for a repeat progesterone level assessment in 2-3 days
- Review subject calendar log and record adverse events as reported by subject or observed by investigator.
- Review instructions for study completion
 - Participants with ovulation are to wait until onset of menses, or two weeks after midluteal visit to complete pregnancy test. Participants with a positive pregnancy test will be moved to pregnancy track.

Record results of serum progesterone in RedCap

